- Have no prevalent diagnosis of Alzheimer's disease or related dementia and not previously screened for AD as part of a research study.
- Family members will be 21 years or older and identified by the patient as the person who would most likely assist with activities of daily living and/or medical decision making if the patient needed assistance.
- See Table 1 for patient and caregiver inclusion and exclusion criteria

Table 1. Inclusion and exclusion criteria for the proposed trial

Inclusion Criteria	
Patients	Family Members
65 years or older	21 years of older
At least one visit to primary care practice within past 24 months	Lives with the patient or lives within a 50 mile radius
Ability to provide informed consent	Ability to provide informed consent
Ability to communicate in English	Ability to communicate in English
	Identified by patient as the person most likely to provide them care if needed
Exclusion Criteria	
Patients	Family Members
Has a diagnosis of AD as determined by ICD-10 code	Is a non-family member who is not a legal Healthcare Power of Attorney
Evidence of a prescription for a cholinesterase inhibitors or memantine	
Has a serious mental illness such as bipolar or schizophrenia as determined by ICD-10 code	Has a serious mental illness such as bipolar or schizophrenia as determined by ICD-10 code
Permanent resident of a nursing facility	Has a diagnosis of AD as determined by ICD-10 code
Is already enrolled in HABC programs	

Recruitment Sites (as of 9/17/18):

- Indiana University Health Primary Care Practices
- Eskenazi Health Primary Care Practices

Primary outcome: Family member quality of life at 24 months.

Co-Primary outcomes: Family member depressive symptoms and family member anxiety at 24 months.

Co-Secondary outcomes: Family member caregiving preparedness and caregiving self-efficacy at 24 months.

Exploratory outcome: Comparison of all outcomes (noted above) between the family members in Screen Only vs. Screen Plus groups.

Table 2. Measures

Outcomes	Construct/Core Attributes	Outcome measure(s)	Name of Measure	Description	Scoring	When	Source
Primary outcome	Family member Quality of Life	Quality of Life	Medical Outcomes Study Short Form Health Survey 36 (SF-36)	36-items that measure health-related quality of life, mental, physical, and social functioning	Scores range 0-100; Higher scores more QOL	Baseline 6 mos. 12 mos. 18 mos. 24 mos.	Family reported Patient reported

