Participants will be recruited from primary care offices affiliated with Eskenazi Health and IU Health.

Step 1: Identification of Potential Participants

- Participants will be identified in a variety of ways and will be tailored based on the recruitment site. Patients will be identified via the Indiana Network for Patient Care, (INPC) which can access patient lists by doctor, clinic, and PC clinic schedules. Physicians will be notified first of their patients' potential eligibility and be asked if the COADS study personnel may approach the patient and their family member for participation. Physicians are routinely given 2 weeks to review the list of their potentially eligible patients (per IU PBRN). Physicians will be given the opportunity to opt-out of study participation at this time. Following either approval from the PCPs, or at the end of the two-week review period study personnel will mail out an introductory letter, email or post card to patients. Study personnel will then approach patients via telephone, email or in person in the-clinic to confirm eligibility and obtain informed consent.
- We will consider any man or woman 65 years or older who has not been diagnosed with AD or related dementia, and is considered an active patient (PCP visit in- person or virtual within 24 months including requests for prescription refills, or questions and is able to provide consent, and speaks English.

- We will approach the primary family member/caregiver/informant for each eligible participant. Family members will be eligible if they are patient-identified or self-identified as a person who is likely to provide care for the patient, is 21 years or older, lives within a 50-mile radius of the participant, is able to consent, and speaks English
- Rolling enrollment will take place over 36 months with an average monthly recruitment of 50 dyads

Step 2: Enrollment

- Following eligibility determination and the informed consent process (including HIPAA release), dyads will be randomly assigned to one of three groups, stratified by site (e.g. Eskenazi or IUH). Dyads are officially enrolled at this point.

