will undergo active surveillance throughout the study via EHR to monitor any AD screening, new diagnoses of AD, and/or new prescriptions for anti-dementia medications. At the 24-month outcome assessment, study personnel will administer the Short Informant Questionnaire on Cognitive Decline in the Elderly (IQCODE) to the family member and the patient will complete the Cognitive Change Index (CCI).

- Rolling enrollment will take place over 36 months with an average monthly enrollment of 50 dyads. The proposed trial will reduce loss to follow-up for longitudinal assessments by engaging the dyads every 6 months throughout the study (6, 12, 18, and 24 months). This includes keeping the assignment of research staff and participants consistent at each outcome assessment, sending reminder letters before each assessment, and sending birthday cards signed by the study team. This strategy has produced a <1% loss to follow-up in the pilot study.

Statistical Plan

Overview

Our study is a three-arm RCT to determine the impact of AD screening on older adults' family members. By design, it will also test the congruence of outcomes between the patient and family member. The 1:1:1 randomization creates three randomized groups.

- For analysis, we will first examine univariate distributions of continuous variables in order to detect any potential violations of assumptions to our planned parametric methods of analyses.
- Variables will be transformed as needed to ensure normal distribution assumptions are met.
- We will use nonparametric methods if transformations are inadequate.
- Demographic characteristics will be compared among the groups in order to evaluate whether the randomization effectively balance the dyads.
- We will use Chi-squared tests or Fisher's exact tests to compare the frequencies of categorical variables. Analysis of variance (ANOVA) or its nonparametric alternative, the Wilcoxon rank sum test, will be used to compare the distribution of continuous variables among the groups.
- All analyses will be conducted using SAS 9.4 (SAS Institute, Carey, North Carolina).

Primary Aim

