- **Multi-level mixed effects models** will be used to examine differences in SF-36 scores for both patients and family members using dyadic analytic approaches. For this aim, we will compare family members in the two screening groups (Screen Only and Screen Plus) to those in the no screening (Control) group. Repeated SF-36 scores from both patients and family members will be included as the outcome variables with participant type (patient or family member), group (Screening Only and Screening Plus versus Control), time, and interaction between groups and time as independent variables. We will use a multi-level variance-covariance matrix in the mixed effects models to account for two sources of potential correlations. Correlations from measures obtained from the same individual over time, an autoregressive correlation will be used. Correlations within a dyad between a patient and his/her family member. A compound symmetry structure will be used for the within-dyad correlation. Parameter estimation and hypothesis tests for the mixed-effects models will be conducted using the maximum likelihood approach that provides robust estimation under the missing at random mechanisms.
- A significant interaction between group and time would indicate differences in changes of SF-36 over time between the two screening groups compared to the no screening group. Absence of significant interactions, significant main group effects will suggest differences in SF-36 between groups' at all follow-up times. For Hypothesis 1 we will use a linear contrast for SF-36 from family members in the combined screening groups (Screen Only and Screen Plus) versus the no screening (Control) group at 24 months. We will also include additional covariates in the mixed effects models to determine whether family member characteristics (relationship to patient, frequency or types of contact, etc.) and knowledge of screening are associated with the outcome measures.

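### The eligibility rules let one person or household enter two separately randomised dyads, which can put screening exposure inside the Control arm

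*Combined protocol and SAP*

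**What the plan says.** **Who may enter as a patient.** Step 1 (Identification of Potential Participants) draws patients from doctor and clinic lists: "We will consider any man or woman 65 years or older", subject to no AD diagnosis, recent primary care contact, consent and English. The Participants list also bars patients who have already had AD screening in research. Table 1 excludes patients already in HABC programs.

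**Who may enter as a family member.** Step 1 says "We will approach the primary family member/caregiver/informant for each eligible participant". That person may be "patient-identified or self-identified as a person who is likely to provide care for the patient". Table 1 accepts a family member who "Lives with the patient or lives within a 50 mile radius". The family-member exclusions concern legal standing, serious mental illness and an AD diagnosis. None concerns existing COADS participation or the family member's own screening.

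**Randomisation.** Under Step 2, "dyads will be randomly assigned to one of three groups, stratified by site". The Statistical Plan overview adds: "The 1:1:1 randomization creates three randomized groups".

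**Analysis.** Under Primary Aim, "Repeated SF-36 scores from both patients and family members will be included as the outcome variables". The covariance has two parts: repeated measures within a person, and patient with family member within a dyad. There is no term for a person or household that appears in two dyads.

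**The concern.** An older couple at one practice can qualify twice: A as patient with B as family member, and B as patient with A as family member. An adult child can be named by both parents. The two dyads are randomised separately.

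The bar on earlier research screening does not close this route. It stops a screened patient from re-entering as a patient. It does not stop that patient from being the family member in a Control dyad, nor a Control family member from enrolling later as a patient.

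The Control arm is meant to show family outcomes when no screening letter has been sent. In discordant linked dyads a letter reaches the Control household, or reaches the Control family member directly. SF-36, PHQ-9 and GAD-7 describe the respondent, so one person's scores can count on both sides of the comparison.

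The planned data would not reveal this. The awareness items in Table 2 ask the family member about the patient's screening, not about their own or another relative's. EHR surveillance in the Control arm follows the Control patients.

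**Working it through.** **Inputs from Statistical Power.** 540 complete dyads per group, so 540 Control against 1,080 combined screening; effect 0.24 SD at 24 months; base correlation 0.2 and decay 0.8; stated power 82.6%. Aim 4: 0.28 SD, 540 against 540, stated 83.4%. Five visits. Alpha is not stated; 0.05 two-sided is assumed.

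**Step 1: reproduce the plan's power.** Take the correlation at lag d as 0.2^(1 + 0.8(d − 1)/3), which gives 0.200, 0.130, 0.085 and 0.055 for lags 1 to 4. Let the difference δ grow linearly from 0 to its 24-month value. With R the correlation matrix and M the contrasts of each later visit with baseline, the multivariate group-by-time F test has 4 numerator df and noncentrality

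λ = (M′δ)′(M′RM)⁻¹(M′δ) / (1/n_C + 1/n_S).

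- Aims 1–3: λ = 12.71, denominator df 1,615, critical F 2.377, power 82.61% (stated 82.6%).
- Aim 4: λ = 12.97, power 83.42% (stated 83.4%).
- Enrolment: 540 / (1 − 0.10) = 600 per group, as stated.

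The stated power is therefore for the interaction test.

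**Step 2: chance that linked dyads differ.** Under independent 1:1:1 allocation:
- one Control and one screened: 2 × 1/3 × 2/3 = 4/9 (44%);
- the other dyad is screened, given that this one is Control: 2/3.

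**Step 3: dilution.** Let q be the share of Control family members linked to one other dyad, and k the fraction of the screening effect that an exposed Control shows. Neither is in the documents; both are assumed. Then

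effect = 0.24 × (1 − k × 2q/3), and λ scales with the square of the effect.

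| q | k = 1: effect (SD) | k = 1: interaction power | k = 0.5: effect (SD) | k = 0.5: interaction power |
|---|---|---|---|---|
| 0 | 0.240 | 82.6% | 0.240 | 82.6% |
| 5% | 0.232 | 79.6% | 0.236 | 81.2% |
| 10% | 0.224 | 76.4% | 0.232 | 79.6% |
| 20% | 0.208 | 69.1% | 0.224 | 76.4% |

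With k = 1, power passes below 80% at q of about 4.5%: 0.045 × 540 ≈ 24 linked Control family members, of whom 2/3 ≈ 16 are exposed.

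**Step 4: the Hypothesis 1 contrast.** For a simple comparison at 24 months, SE = √(1/1080 + 1/540) = 0.0527 SD.
- At 0.24 SD: 0.24/0.0527 = 4.55, power 99.5%.
- At 0.208 SD (q = 20%, k = 1): 0.208/0.0527 = 3.95, power just over 97.6%.

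The estimate shrinks by up to 0.24 − 0.208 = 0.032 SD over this range, but power barely moves.

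**The case against.** **Nothing shows that links occur.** The documents give no count of couples or shared family members. A spouse swap needs both people to be eligible patients, each to be the other's likely carer, and both to take part twice over five visits. Study Design equates 1,900 dyads with 3,800 people, which suggests that distinct individuals were intended, and the Timeline mentions a protocol manual that may hold a duplicate check. This stands as to size: the shares used above are assumptions, and 20% would be 360 of 1,800 dyads. It does not remove the gap, because neither the head count nor an unseen manual is an eligibility rule.

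**Full dilution is too strong for couples.** This stands. In a spouse swap, B's letter concerns B's own cognition, not A's, and there is no clear reason for it to carry the whole effect, least of all on preparedness to care for A. The adult-child case comes closer, since that person receives a letter about a parent. The direction is not certain either: the Background allows that screening may help or harm.

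**A reader might infer that the primary comparison loses material power.** The documents do not support that. The falls in power belong to the multi-df interaction; the 24-month linear contrast named for Hypothesis 1 is hardly affected. Nor is the sample size calculation wrong: it reproduces.

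**A reader might also infer that the omitted correlation must make standard errors too small.** That does not follow. Correlation between linked dyads on the same side adds variance to the contrast; on opposite sides it removes variance. With n per arm, weights of −1/n (Control) and 1/(2n) (screening), and a common correlation, the expected contribution is proportional to (1/9)(1) + (4/9)(1/4) − (4/9)(1/2) = 0. The realised error depends on which links occur.

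**Conclusion.** The gap is real. Followed as written, the plan lets a person or household sit in both Control and a screening arm, and the model has no term for it. The links can contaminate the comparison; the documents do not show that they do. Under the trial's hypothesis the likely bias is toward no difference.

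The size rests on two assumed quantities, the linked share and the strength of exposure, with full strength as the upper bound. Within the range shown, the interaction test can fall below 80% power at quite a small linked share. For the 24-month contrast the matter is an attenuated estimate and dyads wrongly treated as independent. It is worth correcting because the guard is cheap, not because harm has been shown.

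**What to change.** **Prevention.** Add to both columns of Table 1 and to Step 1: already enrolled in COADS in either role, or lives in a household with an enrolled dyad. Check each new dyad against the enrolment log, including shared family members who live elsewhere.

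**Linked dyads already enrolled.**
- Identify and count them, and report the count even if it is nil.
- Keep them in the main analysis in the arm to which they were randomised.
- Account for the shared person or household with a household-level random effect or cluster-robust errors, defining the cluster so that a shared family member joins the two dyads.
- Prespecify a sensitivity analysis that excludes all linked dyads. Keeping only the first-randomised dyad would not do: in about half of discordant pairs that dyad is the exposed Control one.

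The exclusion analysis should stay a sensitivity analysis, because whether a second dyad forms may depend on the first dyad's arm.

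**Cost.** One eligibility line, a log check, a covariance adjustment and one extra analysis, with the loss of a few otherwise eligible second dyads.

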- The multi-level mixed effects models provide a powerful modeling framework for analyzing dyadic outcomes. An alternative model using family member outcomes as the dependent variable and patient outcomes as an independent variable would underestimate variances in outcome measures by ignoring the randomness in the patients' outcomes by treating patient outcomes as fixed covariates. In our proposed models, correlations between patients and their family members on outcome measures (congruence) are explicitly included in the mixed effects models and estimated using maximum likelihood approach. The inclusion of the additional covariance structure due to repeated measures and within dyad correlation also makes it possible to estimate potential differences in patient-family member congruence over time. Comparisons on patient-family member congruence among the groups will be conducted using the likelihood ratio test (LRT) derived from a mixed effects model using group specific correlation structure versus a model using the same correlation in all groups. Changes in congruence can also be conducted using LRT comparing a mixed effects model with time specific correlation structure versus a model using equal correlations across time. By re-aligning data from the family member at specific lag time behind measures from patients, we will also be able to detect a lag effect in family member outcomes using this modeling framework.

Secondary Aim

- **Separate mixed effects models** with PHQ-9 or GAD-7 scores collected at baseline, 6, 12, 18 and 24 months from both patients and family members will be used as the outcome variables for Specific Aim 2. Participant type, randomized group (Screen Only and Screen Plus versus no screening), time and interaction between group and time will be used as independent variables, similarly to the modeling procedures described in details for Aim 1 above. Linear contrasts will be used to compare PHQ-9 and GAD-7 scores from family members in the combined screening groups versus the no screening group at 24 months. Dyad congruence in PHQ-9 and GAD-9 will be examined using LRT from the mixed effects models following the procedure described for Aim 1.

Secondary Aim

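### As listed, the SF-36, PHQ-9 and GAD-7 models give patients and family members one shared group-by-time effect, so the family-member contrast at 24 months estimates a patient/family average

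*Combined protocol and SAP*

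**What the plan says.** In the combined protocol and SAP, the outcome list under Participants gives "Primary outcome: Family member quality of life at 24 months", and it names family-member depressive symptoms and anxiety as co-primary. (Table 2 files those two under secondary outcomes; the label does not affect this point.) Hypotheses 1 and 2 and the power statement also concern family members.

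The model under Statistical Plan, Primary Aim, is dyadic: "Repeated SF-36 scores from both patients and family members will be included as the outcome variables". The independent variables are "participant type (patient or family member), group (Screening Only and Screening Plus versus Control), time, and interaction between groups and time as independent variables". Correlation over time is autoregressive, and for the pair, "A compound symmetry structure will be used for the within-dyad correlation". Hypothesis 1 is then to be tested by a "linear contrast for SF-36 from family members in the combined screening groups" against control at 24 months.

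The first Secondary Aim paragraph, for PHQ-9 and GAD-7, uses the same terms: "Participant type, randomized group (Screen Only and Screen Plus versus no screening), time and interaction between group and time". Nowhere does the plan interact participant type with group or with time. The extra covariates it mentions are family-member characteristics and knowledge of screening. The likelihood ratio tests for congruence concern correlations, not means.

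**The concern.** The declared contrast is for family members, but the listed terms leave the model no way to give family members a treatment effect of their own. A programmer who follows the list will fit one group-by-time profile to both members of the dyad and label the result a family-member effect.

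The trial asks whether screening the patient helps or harms the family member. Under the listed model a family-member effect is pulled toward whatever happens to patients, and an effect confined to patients is reported as a family-member effect. Effects in opposite directions can cancel. The standard error also belongs to the average and not to family members. This affects the primary outcome and both outcomes named as co-primary.

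**Working it through.** **Inputs from the plan.** Five visits (0, 6, 12, 18, 24 months); 1:1:1 allocation; 540 dyads per arm with complete data, so 1,080 screened against 540 control; effect 0.24 SD; linear exponent autoregressive correlation with base 0.2 and decay 0.8; stated power 82.6% (Aims 1–3) and 83.4% (Aim 4, 0.28 SD).

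**Assumptions not in the plan.** Two-sided alpha 0.05; within-dyad correlation ρ = 0.3, range 0 to 0.5; SD 1 in both members unless stated; a group difference growing linearly from 0 at baseline; the patient effects, and the 0.15 SD family effect, used as cases.

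**1. The plan's own power.** Take family-member scores only and the multivariate group-by-time F test with 4 numerator df. The correlations at lags 1 to 4 are 0.200, 0.130, 0.085 and 0.055. The noncentrality is λ = (n₁n₂/(n₁+n₂)) · (Cδ)ᵀ(CRCᵀ)⁻¹(Cδ), where C takes successive differences, R is the correlation matrix and δ is the vector of group differences.
- Aims 1–3: λ = 12.71, denominator df 1,615, power 82.6%.
- Aim 4 (540 vs 540, 0.28 SD): λ = 12.97, power 83.4%.

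Both stated figures are reproduced with a single family-member series.

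**2. What the listed model estimates.** Write each mean as μ + τ(type) + γ(group, time).
- Screened minus control at 24 months for family members is [μ + τ_F + γ(S,24)] − [μ + τ_F + γ(C,24)] = γ(S,24) − γ(C,24).
- For patients, τ_P cancels in the same way and leaves the same expression.

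For the weights, let s = (F + P)/2 and d = F − P for each dyad and visit, where F and P are the family-member and patient scores. With equal variances, s and d are uncorrelated. The group-by-time terms appear only in s and the type term affects d, so the contrast depends on s alone: weight 0.5 on each 24-month score. Solving the generalised least squares equations directly gave 0.5/0.5 at 24 months and 0 at the other visits.

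With unequal SDs, modelled as such, the family weight is (σ_P² − ρσ_Fσ_P)/(σ_F² + σ_P² − 2ρσ_Fσ_P). For σ_F = 1, σ_P = 1.25, ρ = 0.3 this is (1.5625 − 0.375)/(1 + 1.5625 − 0.75) = 0.655, which is still a mixture.

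**3. Standard errors at 24 months.**
- Family only: √(1/1080 + 1/540) = 0.0527.
- Listed model: √[(1/1080 + 1/540)(1 + ρ)/2] = 0.0425 at ρ = 0.3 (0.0373 at 0; 0.0456 at 0.5).

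**4. Rejection probability of the 24-month contrast**, Φ(estimate/SE − 1.96):

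| True effect, SD (family / patient) | Listed model estimate | Listed model rejects | Family-specific rejects |
|---|---|---|---|
| 0.24 / 0 | 0.12 | 81% (75–90%) | 99.5% |
| 0.15 / 0 | 0.075 | 42% (38–52%) | 81% |
| 0 / 0.24 | 0.12 | 81% (75–90%) | 5% |
| 0.24 / −0.24 | 0 | 5% | 99.5% |

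First row at ρ = 0.3: 0.12/0.0425 = 2.82, and Φ(2.82 − 1.96) = 0.81.

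**5. The powered test, group by time.** If only family members respond, halving the effect divides λ by 4, and the smaller variance multiplies it by 2/(1 + ρ). So λ = 12.71 × 0.5/1.3 = 4.89, and power is 39% instead of 82.6% (49% at ρ = 0, 34% at ρ = 0.5).

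**6. Equal effects in both members (0.24 SD).** The listed model estimates 0.24 without bias, and its group-by-time power is 99% / 97% / 94% at ρ = 0 / 0.2 / 0.4.

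**The case against.** The strongest reply is that the authors plainly meant a family-specific contrast: they say so for SF-36, PHQ-9 and GAD-7, and the term list may simply be incomplete. That is probably right about intent. The listed terms still cannot deliver that contrast, and the list is what gets programmed.

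Second, the cases above are chosen to show harm. The documents give no patient effect, and if screening affects both members equally, the pooled contrast is unbiased and more precise (step 6). This stands as a limit on the size of the problem. But equal effects is an assumption that the plan neither states nor tests. The plan itself treats benefit and harm to family members as unknown, and the patient is the one being tested.

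Third, the 0.5 weight needs equal variances and complete data. With an SD ratio of 1.25 and ρ from 0 to 0.4, the estimate in the 0.24/0 case ranges from 0.077 to 0.163 SD instead of 0.12. The amount of attenuation moves; the mixing does not go away.

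Fourth, at the design effect with no patient effect, the 24-month contrast still has about 81% power, near the planned figure. That is true of this one case. It does not help with smaller effects, with the interaction test that the plan actually powers, or with false claims when only patients respond.

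The dyadic covariance is no defence, because it models correlation and not separate mean effects.

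**Conclusion.** The concern holds: the model is wrong as written for SF-36, PHQ-9 and GAD-7. That the family-member and patient contrasts coincide is algebra and needs no numerical assumption. The sizes rest on two-sided 5%, complete data, the stated SDs, a within-dyad correlation of 0 to 0.5 and the assumed patient effects. With equal SDs, half of any difference between the patient and family effects leaks into the reported family effect. The stated power describes a family-only or type-specific analysis, not the model listed. Aim 3 uses family-reported scales and Aim 4 uses family-member scores, so those models are unaffected. This should be corrected before analysis, because it changes what the primary test estimates.

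**What to change.** For SF-36, PHQ-9 and GAD-7, add participant type × time, participant type × group and participant type × group × time. Let residual variances differ by participant type. Define the 24-month contrast (combined screening versus control) explicitly at participant type = family member. Alternatively, fit the confirmatory model to family-member scores alone and keep the dyadic model for the congruence and lag questions. With complete data the two routes give the same family-member contrast.

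With the type-specific terms, the contrast puts weight 1.0 on family-member scores (SE 0.0527). It recovers 0.24 SD whatever the patient effect, rejects 5% of the time when family members have no effect, and has the stated 82.6% power for the group-by-time test.

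The cost is SAP wording and 14 extra fixed-effect parameters with three arms and five visits (4 + 2 + 8), or 9 if the screening arms are pooled in the model (4 + 1 + 4). No new data or participants are needed. What is given up is the extra precision that pooling would bring if the two effects were truly equal.
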